7.1.15. Tissue Specimen Collection and Handling

Tissues collected at biopsy or surgery will be processed according to institutional standard for local histopathological assessment of pancreatic cancer.

See Laboratory Manual for detailed instructions for the preparation, packaging, and shipping instructions for tumor tissue that will be evaluated by IHC for FAP evaluation.

7.1.16. Tumor Burden Assessment

Disease burden will be assessed using RECIST criteria by a central imaging core lab. Local imaging (e.g. CT, MRI, PET/CT) will be anonymized eliminating the PHI, codified with participant study ID, and will be provided to the Sponsor/CRO for third party imaging analysis. Imaging to be submitted is outlined in the Schedule of Activities.

7.2. Adverse Events

7.2.1. Collection Window

For the purposes of this study, the adverse event collection window is from the time of injection with [⁶⁸Ga]FAPI-46 through 24 hours post-injection. If the 24 hour window ends on a holiday or non-clinic day (or the participant cannot return to clinic due to unforeseen circumstances, such as weather), the window may be extended until 72 hours post-injection.

Adverse event collection windows are tied to the number of [⁶⁸Ga]FAPI-46 injections. Cohort 1 will have one AE collection window whereas Cohort 2 will have two discrete AE collection windows.

Any adverse event suspected to be related to [⁶⁸Ga]FAPI-46 – regardless of collection window – should be assessed and reported to the Sponsor/CRO

7.2.2. Definitions

This study defines terms as per the U.S. federal code at 21CFR§312.32:

- **Adverse event**

Any untoward medical occurrence associated with the use of a drug in humans, whether or not considered drug related.

- **Life-threatening adverse event or life-threatening suspected adverse reaction**

An adverse event or suspected adverse reaction is considered "life-threatening" if, in the view of either the investigator or sponsor, its occurrence places the patient or subject at immediate risk of death. It does not include an adverse event or suspected adverse reaction that, had it occurred in a more severe form, might have caused death.

- **Serious adverse event or serious suspected adverse reaction**

An adverse event or suspected adverse reaction is considered "serious" if, in the view of either the investigator or sponsor, it results in any of the following outcomes: Death, a life-threatening adverse event, inpatient hospitalization or prolongation of existing hospitalization, a persistent or significant incapacity or substantial disruption of the ability to conduct normal life functions, or a congenital anomaly/birth defect. Important medical events that may not result in death, be life-threatening, or require hospitalization may be considered serious when, based upon appropriate medical judgment, they may jeopardize the patient or subject and may require medical or surgical intervention to prevent one of the outcomes listed in this definition. Examples of such medical events include allergic bronchospasm requiring intensive treatment in an emergency room or at home, blood dyscrasias or convulsions that do not result in inpatient hospitalization, or the development of drug dependency or drug abuse.

- **Suspected adverse reaction**

Any adverse event for which there is a reasonable possibility that the drug caused the adverse event. For the purposes of IND safety reporting, "reasonable possibility" means there is evidence to suggest a causal relationship between the drug and the adverse event. Suspected adverse reaction implies a lesser degree of certainty about causality than adverse reaction, which means any adverse event caused by a drug.

- **Unexpected adverse event or unexpected suspected adverse reaction**

An adverse event or suspected adverse reaction is considered "unexpected" if it is not listed in the investigator brochure or is not listed at the specificity or severity that has been observed; or, if

an investigator brochure is not required or available, is not consistent with the risk information described in the general investigational plan or elsewhere in the current application, as amended. For example, under this definition, hepatic necrosis would be unexpected (by virtue of greater severity) if the investigator brochure referred only to elevated hepatic enzymes or hepatitis. Similarly, cerebral thromboembolism and cerebral vasculitis would be unexpected (by virtue of greater specificity) if the investigator brochure listed only cerebral vascular accidents. "Unexpected," as used in this definition, also refers to adverse events or suspected adverse reactions that are mentioned in the investigator brochure as occurring with a class of drugs or as anticipated from the pharmacological properties of the drug, but are not specifically mentioned as occurring with the particular drug under investigation.

- **Severity Grading**

Adverse event severity will be evaluated utilizing the CTCAE v.5 criteria. If there is a question regarding severity grading or harmonization, the Sponsor or CRO should be contacted.

7.2.3. Reporting Adverse Events

- **Routine adverse events**

Adverse events that do not meet serious criteria (section 8.4) are considered routine adverse events. Routine adverse events are reported utilizing the appropriate eCRF page in the study database.

The investigator is reminded to comply with all institutional and local requirements as well as the requirements put forth by the IRB of record regarding reporting of routine adverse events.

- **Serious adverse events**

Any adverse event meeting serious criteria (section 8.2) occurring within the collection window must be reported following the instructions in Appendix 1 – Serious Adverse Event Reporting. **The timeframe for reporting** the event to the sponsor/CRO is **1 business day** of the clinical investigator becoming aware of the initial event or clinically significant follow-up information.

The Investigator must provide a causality assessment and must sign and date all SAE Report Forms.

If supporting documentation is included in the submission (e.g., hospital reports, consultant reports, death certificates, autopsy reports, etc.), all protected health information must be redacted. When appropriate, additional written reports and supporting documentation will be provided by the site for further clarification and information.

The investigator is reminded to comply with all institutional and local requirements as well as the requirements put forth by the IRB of record regarding serious adverse events.

- **Adverse events leading to study discontinuation**

Participants who have withdrawn, or were withdrawn, from the study due to an adverse event (regardless of attribution) will be followed by the investigator until resolution or a new baseline, provided the participant consents to being followed.

- **Attribution to Investigational Medical Product and Study Procedure**

The relationship of [⁶⁸Ga]FAPI-46 and the PET scan procedure to an adverse event will be assessed by the Investigator utilizing the FDA's December 2012 guidance *Safety Reporting Requirements for INDs and BA/BE Studies*.

The investigator must note if there is a reasonable possibility there is evidence to suggest a causal relationship between [⁶⁸Ga]FAPI-46 and the adverse event and if there is evidence to suggest a causal relationship between the PET scan procedure and the adverse event.

Within the reporting requirement under 21 CFR§312.32(c)(1)(i), FDA makes clear the meaning of reasonable possibility by providing the following examples of types of evidence that would suggest a causal relationship between the drug and the adverse event.

- A single occurrence of an event that is uncommon and known to be strongly associated with drug exposure (e.g., angioedema, hepatic injury, Stevens-Johnson Syndrome)
- One or more occurrences of an event that is not commonly associated with drug exposure, but is otherwise uncommon in the population exposed to the drug (e.g., tendon rupture)
- An aggregate analysis of specific events observed in a clinical trial (such as known consequences of the underlying disease or condition under investigation or other events that those events occur more frequently in the drug treatment group than in a concurrent or historical control group)

Although the sponsor is responsible for determining whether there is a reasonable possibility that the drug caused the adverse event, taking into consideration the investigator's assessment, the FDA requires the clinical investigator provide the sponsor with their assessment of causality for all serious adverse events.

- **Laboratory Abnormalities**

All abnormal laboratory results pre-categorized within the CTCAE v5 meeting grade 3 or 4 severity will be recorded and reported as AEs.

An abnormal laboratory result pre-categorized within the CTCAE v5 meeting grade 1 or 2 severity will be recorded and reported as an AE if the investigator deems the result clinically significant.

An abnormal laboratory result not pre-categorized within the CTCAE v5 (e.g., increased eosinophils, decreased creatinine) will not be captured as an adverse event unless deemed clinically significant by the investigator. The investigator must deem the result "mild," "moderate," "severe," or "life threatening," with the clinically significant notation.

- **Clinical Syndrome/Diagnosis vs. Symptomatic Components**

To the extent possible, individual symptomatic events (i.e., nausea, vomiting, laboratory abnormalities) observed during the course of the study should be reported as the overarching syndrome/diagnosis rather than the individual symptoms. For example, 'refeeding syndrome,' 'renal failure,' or 'hepatitis.' As appropriate, the laboratory abnormality itself (e.g., elevated creatinine) does not need to be recorded as an AE. Final determination of the appropriateness of recording (i.e. syndrome/diagnosis vs. symptom) is made by the clinical investigator.

- **Reporting Adverse Events to Participants**

The Sponsor will review all reported serious adverse events and determine the appropriateness of changes to the informed consent document. The sponsor will notify investigators if re-consenting subjects is mandatory for all participants or only for those currently undergoing investigational procedures. If the sponsor does not believe re-consenting is mandatory, the investigator may require re-consent for those all participants or just those subjects undergoing investigational procedures. Similarly, the sponsor will also defer to the IRB of record if it determines re-consent should be mandatory.

7.2.4. Documentation

Case Histories / Participant Binders

Adverse events should be recorded within the participant's case book / study binder compliant

with ALCOA. At minimum, information captured must include:

- Term, harmonized to CTCAE v. 5. Do not use a verbatim term or medical jargon – for example, use “white blood cell decreased,” instead of *leukopenia* and “neutrophil count decreased,” rather than *neutropenia*.
- Severity grade (as per CTCAE v. 5)
- Date, onset
- Date, end
- Outcome (e.g., without sequelae, with sequelae, ongoing)
- Attribution to study drug (unrelated, probable, definite)
- Attribution to the study procedure (i.e., PET/CT scan) (unrelated, probable, definite)

Attributions must be confirmed by the study’s clinical investigator and documented by signature and date.

7.3. Unanticipated Problems

The phrase “unanticipated problems involving risks to subjects or others” is found but not defined in the HHS regulations at 45 CFR part 46. OHRP considers unanticipated problems, in general, to include any incident, experience, or outcome that meets **all** of the following criteria:

- Unexpected in terms of nature, severity, or frequency given (a) the research procedures that are described in the protocol-related documents, such as the Institutional Review Board (IRB)-approved research protocol and informed consent document; and (b) the characteristics of the participant population being studied;
- Related or possibly related to participation in the research (“possibly related” means there is a reasonable possibility that the incident, experience, or outcome may have been caused by the procedures involved in the research); and
- Suggests that the research places participants or others at a greater risk of harm (including physical, psychological, economic, or social harm) than was previously known or recognized.

OHRP recognizes that it may be difficult to determine whether a particular incident, experience, or outcome is unexpected and whether it is related or possibly related to participation in the research. OHRP notes that an incident, experience, or outcome that meets the three criteria above generally will warrant consideration of substantive changes in the research protocol or informed consent process/document or other corrective actions in order to protect the safety, welfare, or rights of subjects or others

Only a small subset of adverse events occurring in human subjects participating in research will meet these three criteria for an unanticipated problem.

Furthermore, there are other types of incidents, experiences, and outcomes that occur during the conduct of human subjects research that represent unanticipated problems but are not considered adverse events. For example, some unanticipated problems involve social or economic harm instead of the physical or psychological harm associated with adverse events. In other cases, unanticipated problems place subjects or others at increased risk of harm, but no harm occurs. Examples of unanticipated problems (UP) provided by OHRP:

- Clinical trial data are stored on a laptop computer without encryption, and the laptop computer is stolen from the investigator’s car on the way home from work.
- As a result of a processing error by a pharmacy technician, a subject enrolled in a multicenter clinical trial receives a dose of an experimental agent that is 10-times higher than the dose dictated

by the IRB-approved protocol. While the dosing error increased the risk of toxic manifestations of the experimental agent, the subject experienced no detectable harm or adverse effect after an appropriate period of careful observation.

- Subjects with cancer are enrolled in a phase 2 clinical trial evaluating an investigational biologic product derived from human sera. After several subjects are enrolled and receive the investigational product, a study audit reveals that the investigational product administered to subjects was obtained from donors who were not appropriately screened and tested for several potential viral contaminants, including the human immunodeficiency virus and the hepatitis B virus.

7.3.1. Deviation from prescribed dose

In accordance with the NRC guidelines for diagnostic Nuclear Medicine, in the event of deviations from prescribed administered dose activity, the CRO/Sponsor should be contacted within 1 business day. This single intravenous (IV) injection should contain $5 \text{ mCi} \pm 2 \text{ mCi}$ of $[^{68}\text{Ga}]\text{FAPI-46}$ and a maximum mass dose of $< 60 \text{ }\mu\text{g}$. The total volume administered will be between 1 and 10 mL. A protocol violation will be considered when $[^{68}\text{Ga}]\text{FAPI-46}$ dose administered is more than 20% of the prescribed activity.

If the dose deviation is reasonably associated with an adverse event (serious or non-serious), documentation for the adverse reaction must also be completed regardless of adverse reaction onset.

The investigator is reminded to comply with all institutional and local requirements as well as the requirements put forth by the IRB of record regarding protocol violations.

7.3.2. Pregnancy

A pregnancy occurring in a participant or in the partner of a participant during the course of the study (i.e. from study drug injection until end of study participation) is considered an unanticipated problem.

The investigator or site personnel must notify the Sponsor within 5 working days after the investigator or site personnel become aware of the pregnancy (see APPENDIX 1 – SERIOUS ADVERSE EVENT REPORTING for details). If an SAE occurs in conjunction with the pregnancy, then the reporting time frame for an SAE (within 1 business day) must be met.

The investigator is reminded to comply with all institutional and local requirements as well as the requirements put forth by the IRB of record regarding a pregnancy during trial participation.

7.3.3. Unanticipated Problem Reporting Adverse event as an unanticipated problem

An adverse event, or serious adverse event, also meeting the definition of an unanticipated problem will follow the adverse event reporting pathway.

7.3.4. Investigator-identified non-adverse event unanticipated problems

The investigator will provide information to the sponsor-investigator within 1 business day. The report will include the following information:

- Protocol identifying information: protocol title and number, investigator's name, and the participant study ID (if applicable)
- A detailed description of the event, incident, experience, or outcome;
- An explanation of the basis for determining that the event, incident, experience, or outcome represents an UP

- A description of corrective actions that have been taken or are proposed in response to the UP or proposed changes to the protocol or investigational plan

The investigator is reminded to comply with all institutional and local requirements as well as the requirements put forth by the IRB of record regarding unanticipated problems.

7.3.5. Reporting Unanticipated Problems to Participants

The sponsor will review all unanticipated problems and determine the appropriateness of changes to the informed consent document. The sponsor will notify investigators if re-consenting subjects is mandatory for all participants or only for those currently undergoing investigational procedures.

The sponsor will defer to these IRBs if requested to change the risk section of the informed consent document. Similarly, the sponsor will also defer to the IRBs if it is determined re-consent should be mandatory.

8. STATISTICAL ANALYSIS

8.1. General

Descriptive statistics will be utilized for safety parameters. All patients will be accounted for. The study population for all analyses will be defined as all patients enrolled in the study who receive at least one dose of [⁶⁸Ga]FAPI-46. Patients who exit the study prior to receiving study medication may be replaced.

For this study, the primary efficacy endpoints are sensitivity and specificity, each of which will be evaluated with a hypothesis test:

H_0 : Sensitivity (Specificity) \leq Performance Goal (PG)

H_1 : Sensitivity (Specificity) $>$ Performance Goal (PG)

Where success is defined as rejecting the null hypothesis for the sensitivity hypothesis tests. The specificity test will have lower power given the lower number of samples that are likely to be negative from the histopathology sample.

The minimum sample size necessary to achieve desired power for sensitivity was computed for the hypothesis test above utilizing a one-sample binomial proportion test with a normal approximation, an upper one-sided significance level of 0.05, and the following parametric assumptions:

- Performance Goal (PG) = 0.75 for sensitivity and 0.70 for specificity
- True Sensitivity and Specificity = 0.90

Given the parametric assumptions above, 60 subjects will yield 92.7% power to demonstrate that the true sensitivity and specificity is greater than 0.75.

Additional exploratory data analyses will be conducted as deemed appropriate by the Sponsor.

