6.1. Study Design

This is a prospective, multi-center, single arm, open label, non-randomized study to evaluate the ability of [^{68}Ga]FAPI-46 to detect FAP expressing cells in patients with resectable or borderline resectable PDAC. The [^{68}Ga]FAPI-46 PET scans will be acquired after initial staging using institutional standard methods. If the participant is prescribed neoadjuvant therapy, a second [^{68}Ga]FAPI-46 PET scan will be performed within 21 days prior to planned surgical resection. This will be followed by histopathology and IHC analyses and comparison to resected PDAC tumor specimens. The surgeon will not be blinded to the [^{68}Ga]FAPI-46 scans prior to surgery.

Experimental Design: Phase 2, prospective, multi-center, single arm, non-randomized, open label study

Allocation of treatment: open-label, non-randomized, single intervention

Number of patients planned: Up to 60 patients will be enrolled. Participants who withdraw, are withdrawn, do not complete the [⁶⁸Ga]FAPI-46 PET scan ≤ 21 days prior to surgery (Cohort 2), do not have a core biopsy prior to NAT or who are not surgical candidates post-NAT (Cohort 2) may be replaced at the discretion of the sponsor.

Summary of Study Visits and Data Collection: Refer to Schedule of Events for full requirements for each visit. The Schema provides a graphical representation of the study visits.

All participants

Screening: Screening assessments can be conducted at multiple visits provided they are within 28 days prior to study day 1, including anatomic imaging. Tests performed for standard of care may be used for screening purposes provided they are within window.

Visit 1: Defines Study Day 1. [⁶⁸Ga]FAPI-46 PET scan obtained.

Visit 2: 24 to 72 hours after [⁶⁸Ga]FAPI-46 injection. Safety assessment with safety labs and, if needed, a symptom directed physical examination. This is the last active study-related event with the participant.

Cohort 1 only: Participants in Cohort 1 are those not prescribed neoadjuvant therapy and directly undergo surgical resection within 21 days post-[⁶⁸Ga]FAPI-46 PET scan. Data will be mined from the medical records regarding the surgical procedure and pathologic outcomes. The final study-directed visit is Visit 2.

Surgery: Surgical resection to occur within 21 days after [⁶⁸Ga]FAPI-46 PET scan. Resected tissue should be collected as per laboratory manual. Surgical and pathology reports will be collected, codified, and provided for study.

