6.1.2 Justification of Sample Size

The sample size is 60 patients in order to adequately power the primary objective of sensitivity.

For this study, the primary efficacy endpoints is sensitivity, evaluated with a hypothesis test:

H0: Sensitivity \leq PG

H1: Sensitivity $>$ PG

The minimum sample size necessary to achieve power for sensitivity was computed for the hypothesis test above utilizing a one-sample binomial proportion test with a normal approximation, an upper one-sided significance level of 0.05, and the following parametric assumptions:

- PG = 0.75 for sensitivity
- True Sensitivity = 0.90

Given the parametric assumptions above, 60 patients yields 92.7% power to demonstrate that the true sensitivity is greater than 0.75.

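### Protocol 8.1 attributes the 92.7% power to specificity as well as sensitivity, but the figure belongs to sensitivity alone

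*Protocol*

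**What the plan says.** Protocol 8.1 names sensitivity and specificity as primary efficacy endpoints, each with its own hypothesis test. It gives these inputs:

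- Test: "utilizing a one-sample binomial proportion test with a normal approximation", with "an upper one-sided significance level of 0.05".
- Goals: "Performance Goal (PG) = 0.75 for sensitivity and 0.70 for specificity".
- Assumed truth: "True Sensitivity and Specificity = 0.90".

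It introduces the calculation as one for sensitivity and warns: "The specificity test will have lower power given the lower number of samples that are likely to be negative". It then concludes that "60 subjects will yield 92.7% power to demonstrate that the true sensitivity and specificity is greater than 0.75".

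The Protocol synopsis gives the same 92.7% for sensitivity only. It also says that the sample size is based on sensitivity because few samples are expected to be available for testing specificity. SAP 6.1.2 likewise says that "60 patients yields 92.7% power to demonstrate that the true sensitivity is greater than 0.75". SAP Section 8 removes specificity and accuracy from the primary endpoint.

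On numbers, Protocol 6.1 says "Up to 60 patients will be enrolled", with replacement of certain participants at the sponsor's discretion. Neither document states an allowance for non-evaluable patients.

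**The concern.** Three statements in Protocol 8.1 do not fit together. One power figure is given for two parameters, although their goals differ (0.75 and 0.70). The figure is given for specificity, although the text says the calculation was made for sensitivity. And 92.7% is claimed for a test that the same section describes as having lower power.

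The main statistical section therefore credits a named primary endpoint with an operating characteristic that the design does not have. Someone who cites that sentence alone would take specificity to be a powered endpoint.

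**Working it through.** **1. Reproduce 92.7%.** The inputs are in Protocol 8.1: p0 = 0.75, p1 = 0.90, one-sided alpha 0.05 (critical value 1.645), n = 60. The test statistic with the null standard error is z = (x/n − p0) / √(p0(1 − p0)/n), and √(0.75 × 0.25/60) = 0.0559.

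- x = 50: (0.8333 − 0.75)/0.0559 = 1.49, do not reject.
- x = 51: (0.85 − 0.75)/0.0559 = 1.79, reject.

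The rule is to reject at 51 or more of 60. P(X ≥ 51 | 60, 0.90) = 0.9269, with actual size P(X ≥ 51 | 60, 0.75) = 0.0452. This matches the stated 92.7%. The closed-form normal approximation, Φ[(0.15 − 1.645 × 0.0559)/√(0.90 × 0.10/60)], gives 0.933. The number itself is sound.

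**2. See whether it can be the specificity figure.** Specificity is tested against 0.70. Even if all 60 units were histopathology-negative, the stated test would reject at 48 or more with power 99.4%; an exact 5% rule (49 or more) gives 98.5%. So 92.7% is not the specificity power at n = 60 with the stated goal. It would arise only with 60 negatives tested against 0.75, the sensitivity goal. And 60 subjects with one sample each cannot supply both 60 positives and 60 negatives.

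**3. Specificity power with few negatives.** The number of negatives, m, is an assumption. Goal 0.70, true value 0.90, z = (x/m − 0.70)/√(0.21/m).

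| Negatives m (assumed) | Result needed to reject | Check | Power |
|---|---|---|---|
| 6 | none possible | 6/6 gives 0.30/√(0.21/6) = 1.60 | 0 |
| 10 | 10/10 | z = 2.07; 9/10 gives 1.38 | 0.90^10 = 34.9% |
| 15 | 14/15 or better | z = 1.97; 13/15 gives 1.41 | 54.9% |
| 20 | 18/20 or better | z = 1.95; 17/20 gives 1.46 | 67.7% |

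Power does not rise smoothly at these sizes because the outcomes are discrete. With 8 negatives a perfect result rejects, but the actual size is then 0.70^8 = 5.8%, above the nominal level. An exact 5% test cannot reject with 8 or fewer.

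**4. Sensitivity with fewer than 60 evaluable positives.** The evaluable counts are again assumptions. The rule is as in step 1; at these counts the stated test and an exact 5% rule have the same cut-off.

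| Evaluable positives (assumed) | Reject at | Power |
|---|---|---|
| 60 | 51 | 92.7% |
| 55 | 47 | 90.6% |
| 50 | 43 | 87.8% |
| 45 | 39 | 84.2% |

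**The case against.** The strongest reply is that the slip is already contained. Protocol 8.1 carries its own warning about specificity. The synopsis and SAP 6.1.2 give 92.7% for sensitivity only, the SAP drops specificity from the primary endpoint, and both documents define success by sensitivity alone. No primary decision turns on the two stray words. This stands, and it is why the point is minor. It does not make the sentence correct.

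A reader might also infer that the sensitivity power is overstated because patients without matched histopathology will drop out of the analysis. The documents do not establish this. SAP 7.1.2.1 does ask for a corresponding histopathology result, but SAP 7.1.2 and 9.4 treat missing or invalid histopathology as positive for the primary region, which would keep such patients in the denominator. The clear source of loss among dosed patients is uninterpretable PET, for which no rate is given. The statement for 60 patients is true if 60 are evaluable, and at an assumed 55 power is still about 91%. The dependence on 60 evaluable deserves a clarifying note; it is not an error.

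A reader might further infer that negatives must be close to zero because every patient has confirmed PDAC. That follows from the SAP's per-patient endpoint on the primary lesion. Protocol 5.2.1 counts lesions, and other sampled lesions could be negative. The Protocol supports only a small number of negatives.

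**Conclusion.** The power sentence in Protocol 8.1 is wrong as written. It is an internal inconsistency of minor weight, not an arithmetic error: 92.7% is right for sensitivity with 60 evaluable histopathology-positive units and is misattributed to specificity.

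Under the stated test with goal 0.70 and true value 0.90, specificity power is zero with 6 or fewer negatives and about 35%, 55% and 68% with 10, 15 and 20. Those counts are illustrations, since the documents give none. The conclusion that the sentence is wrong does not depend on them: it follows from the 0.70 goal and from the section's own statement that specificity power is lower.

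The documents do not support a wider conclusion that the trial is underpowered for its primary analysis. Sensitivity power stays at about 84% even with an assumed 45 evaluable positives.

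**What to change.** In Protocol 8.1, delete the words *and specificity* from the power sentence so that it agrees with the synopsis and SAP 6.1.2, and state that the specificity test (goal 0.70) is not powered.

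Optional note, in Protocol 8.1 and SAP 6.1.2: say that 92.7% assumes 60 evaluable histopathology-positive patients, and give about 91%, 88% and 84% at an assumed 55, 50 and 45. The Protocol wording should not cite EFFS1, which is defined only in the SAP. Alongside this, reconcile the EFFS1 definition in SAP 7.1.2.1, which requires a histopathology result, with SAP 7.1.2 and 9.4, which treat a missing result as positive, so that it is clear who counts as evaluable.

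The cost is wording only. Design, sample size and planned test are unchanged.
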